1 PROTOCOL SUMMARY

Full Title	Randomized Multi-Center Study Comparing No Drainage to Preoperative Biliary Drainage Using Metal Stents in Patients with Resectable Pancreatic or Periapillary Cancer
Short Title	Preoperative Biliary Drainage RCT
Objective(s)	To demonstrate that preoperative biliary drainage using self-expanding metal stents (SEMS) improves overall surgical outcomes in patients undergoing pancreaticoduodenectomy for treatment of pancreatic or periampullary cancer.
Test Device	
Devices:
 
WallFlex Biliary RX Fully Covered stent
 
Note: WallFlex Biliary RX Uncovered stents may be used in some cases as outlined in the protocol
 
Cleared Indication:
 
The WallFlex Biliary stents are indicated for use in the palliative treatment of biliary strictures produced by malignant neoplasms; the WallFlex FC stent is also indicated for the treatment of benign biliary strictures per CE Mark.

Study Design	
 • Prospective, multi-center, randomized, post-market (on label) • Patients will be block randomized at baseline in a 1:1 ratio between Group 1: No Pre-Operative Biliary Drainage and Group 2: Pre-Operative Biliary Drainage with a SEMS.
Planned Number of Subjects	
294 total number of subjects:
 
 • Group 1: 147 • Group 2: 147
Planned Number of Centers / Countries	
7-12 sites
 
Countries: Australia, Belgium, China, France, Germany, India, Italy, Japan (this list of countries may change)

Primary Endpoint	Serious pre-operative, operative and post-operative adverse events to 120 days post randomization or to 30 days post-surgery, whichever comes last


Secondary Endpoints
	
 1. Adverse events: rate, severity, seriousness, relatedness to stent or endoscopic or surgical procedure, impact on time of surgery, length of hospitalization and ICU stay 2. Time to surgery 3. Curative Intent Surgery details pertaining to intraoperative assessment of resectability, surgical resection and reconstruction techniques 4. Intraoperative blood loss and blood transfusions, duration of surgery 5. Biliary obstructive symptoms assessment (Week 2, surgery/transition to palliation, 30 day post-operative follow up and 120 day follow up) 6. Improvement of LFT levels as relative to baseline (Week 2, surgery/transition to palliation, 30 day post-operative follow up and 120 day follow up) 7. Stent placement success: ability to deploy the stent in satisfactory position across the stricture (Group 2) 8. Stent removal success: successful SEMS removal, either en bloc at time of surgery or endoscopically prior to surgery without stent removal related SAEs 9. Number, type, reason and timing of biliary re-interventions 10. Number and duration of hospital and ICU admissions

Follow-up Schedule and Assessments
	
 • Screening: Count all consecutive patients seen at investigational site presenting with biliary obstructive symptoms and suspicion of pancreatic cancer, distal common bile duct cholangiocarcinoma or peri-ampullary cancer. Of those, a subset will be invited to participate in trial: Informed Consent (enrollment) and Eligibility Criteria Assessment • Baseline Visit (Day 0): Demographics, Medical History, Tumor Diagnosis, Staging and Characteristics, Assessment of Biliary Obstructive Symptoms, Laboratory Tests, Randomization • Stent Placement Procedure Visit (Group 2 only, Day 0): Stent Details, Procedure Details, Adverse Events (AEs) • Pre-Operative Visit (Week 2): Assessment of Biliary Obstructive Symptoms, Laboratory Tests, AEs 
Group 1 (No Pre-Operative Biliary Drainage): Patients will undergo resection per institutional standard of practice. Time to surgery is not to exceed 4 weeks unless there is a need to delay

	
planned surgery due to a complication, biliary obstructive symptoms, decline in patient physiologic status, or other factors that preclude surgery.
 
Group 2 (Pre-Operative Biliary Drainage with a SEMS): Patients will undergo resection after resolution of jaundice is achieved (defined as Bilirubin below 100µmol per liter), or at 4 weeks, whichever comes first.
 
 • Biliary Reintervention Visit (as needed): Timing, Reason for Biliary Reintervention, Type of Biliary Reintervention, AEs Group 1 patients who fail their treatment algorithm by requiring biliary drainage prior to surgery will receive a study SEMS. Group 2 patients who require re-stenting or placement of a stent for a new stricture, will receive a study SEMS. • Curative Intent Surgery: Assessment of Biliary Obstructive Symptoms, Laboratory Tests, Operative Details, Stent Removal, Blood Loss, Intra- and Post-Operative Transfusion, Post-Operative Course, Specimen Pathology, AEs • Transition to Palliative Management Visit (as needed): Assessment of Biliary Obstructive Symptoms, Laboratory Tests, AEs • Post-Operative Follow up Visit (30 days Post-Surgery, if applicable): Assessment of Biliary Obstructive Symptoms, Laboratory Tests, AEs • Long Term Follow-up Visit (120 days--150 days post randomization): Assessment of Biliary Obstructive Symptoms, Laboratory Tests, AEs 
Patients who undergo surgery as planned will be evaluated at 30 days post-surgery and will be followed up to 120 days after randomization.
 
Patients with delay in planned surgery may require follow up longer than 120 days to allow for a 30 day post-surgery follow up visit but follow up is not to exceed 150 days post-randomization.
 
Patients with a delay in planned surgery whose rescheduled surgery is unable to occur within 120 days will be followed up to 120 days after randomization.
 
Patients who do not undergo surgery as planned due to conversion to palliative management or patient choice will be followed up to 120 days after randomization. If patient's course of treatment requires placement of a biliary stent, stenting will be done per

--	---

	
standard of care at each institution. If a metal stent is required, a study WallFlex Biliary FC stent will be placed.


Key Inclusion Criteria
	
 1. Age 18 or older 2. Willing and able to comply with the study procedures and provide written informed consent to participate in the study 3. Diagnosis of probable pancreatic cancer, distal common bile duct (CBD) cholangiocarcinoma and other periampullary cancers (histology not required) 4. Biliary obstructive symptoms or signs 5. Bilirubin level at/above 100 μmol per liter (5.8 mg/dL) 6. Distal biliary obstruction consistent with pancreatic cancer, distal CBD cholangiocarcinoma or other periampullary malignancy 7. Location of distal biliary obstruction is such that it would allow the proximal end of a stent to be positioned at least 2 cm from the hilum 8. Patients deemed as resectable by pancreatic protocol CT or MRI 9. Surgical candidate per pancreatobiliary surgeon after multi-disciplinary discussion 10. Surgery intent within 4 weeks 11. Endoscopic and surgical treatment to be provided by same team

Key Exclusion Criteria
	
 1. Biliary strictures caused by confirmed benign tumors 2. Biliary strictures caused by malignancies other than pancreatic, cancer, distal CBD cholangiocarcinoma and other periampullary cancers 3. Surgically altered biliary tract anatomy, not including prior cholecystectomy 4. Neoadjuvant chemotherapy for current malignancy 5. Palliative indication due to reasons other than surgical candidate status 6. Previous biliary drainage by ERCP/PTC 7. Patients for whom endoscopic techniques are contraindicated 8. Participation in another investigational trial within 90 days

	9. Pregnancy
Primary Statistical Hypothesis	
A literature search of preoperative biliary drainage with self-expanding metal stents in patients with pancreatic or periampullary cancer yielded eight articles with 305 patients.¹⁻⁸
 
A meta-analysis of the probability for pre-operative, operative and peri-operative complications was performed. A rate of 24.2% [95% CI: 13.2%, 37.2%] was calculated using the eight articles.
 
Statistical testing will be performed to determine if the rate of complications for the Pre-Operative Biliary Drainage with SEMS group is non-inferior to the No Pre-Operative Biliary Drainage group. The null hypothesis is that the complication rate is inferior in the Pre-Operative Biliary Drainage with SEMS versus the No Pre-Operative Biliary Drainage group:
 
$H_0: \pi_{test} - \pi_{control} \geq \Delta$ (Inferior)
 
$H_a: \pi_{test} - \pi_{control} < \Delta$ (Non-inferior)
 
where π_{test} and $\pi_{control}$ are the probabilities of having pre-operative, operative and peri-operative complications in the Pre-Operative Biliary Drainage with SEMS arm and No Pre-Operative Biliary Drainage arm respectively, and Δ is defined as the non-inferiority margin.
 
The sample size was calculated for a one-sided 0.050 exact Farrington-Manning test using StatXact 9®. If the P value from the exact Farrington-Manning test is <0.05 then the Pre-Operative Biliary Drainage with SEMS group will be considered non-inferior to the No Pre-Operative Biliary Drainage group. The expected probability of complications in the Pre-Operative Biliary Drainage with SEMS arm and No Pre-Operative Biliary Drainage arm is 37.2%, which was taken from the upper limit of the 95% CI from the meta-analysis described above and from the only available Level 1 study comparing no drainage to preoperative stenting in which the complication rate was reported to be 39% in the no drainage arm.⁹ The non-inferiority margin (Δ) is 15%. Given these assumptions and a one-sided 5% significance level, $2 \times 132 = 264$ subjects will provide 80% power to reject the null hypothesis, that the Pre-Operative Biliary Drainage with SEMS group is inferior to the No Pre-Operative Biliary Drainage group.
 
To compensate for possible loss of subjects after enrollment and

	complete assessment of inclusion/exclusion criteria, an additional 10% of subjects will be enrolled, for a total of $2 \times 147 = 294$ subjects.
--	--

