3 ENDPOINT ANALYSIS

3.1 Primary Endpoint

The rate of serious adverse events is the primary endpoint for the study.

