3.1.1 Hypotheses

Statistical testing will be performed to determine if the rate of complications for the Pre-Operative Biliary Drainage with SEMS group is non-inferior to the No Pre-Operative Biliary Drainage group. The null hypothesis is that the complication rate is inferior in the Pre-Operative Biliary Drainage with SEMS versus the No Pre-Operative Biliary Drainage group:

$$H_0: \pi_{\text{test}} - \pi_{\text{control}} \geq \Delta \text{ (Inferior)}$$

$$H_a: \pi_{\text{test}} - \pi_{\text{control}} < \Delta \text{ (Non-inferior)}$$

where π_{test} and π_{control} are the probabilities of having pre-operative, operative and peri-operative complications in the Pre-Operative Biliary Drainage with SEMS arm and No Pre-Operative Biliary Drainage arm respectively, and Δ is defined as the non-inferiority margin.

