3.1.2 Sample Size

A literature search of preoperative biliary drainage with self-expanding metal stents in patients with pancreatic or periampullary cancer yielded 8 articles with 305 patients.^{21-24, 27-31}

The following meta-analysis of the probability for pre-operative, operative and post-operative complications was done:

- A rate of 24.2% [95% CI: 13.2%, 37.2%] was calculated using the 8 articles.

The sample size was calculated for a one-sided 0.050 exact Farrington-Manning test using StatXact 9®. If the P value from the exact Farrington-Manning test is <0.05 then the *Pre-Operative Biliary Drainage with SEMS* group will be considered non-inferior to the *No Pre-Operative Biliary Drainage* group. The expected probability of complications in the *Pre-Operative Biliary Drainage with SEMS* arm and *No Pre-Operative Biliary Drainage* arm is 37.2%, which was taken from the upper limit of the 95% CI from the meta-analysis described above and from the only available Level 1 study comparing no drainage to preoperative stenting in which the complication rate was reported to be 39% in the no drainage arm.⁹ The non-inferiority margin (Δ) is 15%. Given these assumptions and a one-sided 5% significance level, $2 \times 132 = 264$ subjects will provide 80% power to reject the null hypothesis, that the *Pre-Operative Biliary Drainage with SEMS* group is inferior to the *No Pre-Operative Biliary Drainage* group.

To compensate for possible loss of subjects after enrollment and complete assessment of inclusion/exclusion criteria, an additional 10% of subjects will be enrolled, for a total of $2 \times 147 = 294$ subjects.

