3.1.3 Statistical Methods

For calculating the rate of serious adverse events after randomization, patients with insufficient follow-up will be excluded from the calculation; that is, only patients that have at least follow-up through the long term visit (120/150 day follow-up) will be included unless the subject has already had a serious adverse event. All patients with a serious adverse will be counted in the analysis. Sensitivity analyses, such as a tipping point analysis will be performed to assess the impact of the missing data, assuming extremes of either no SAEs or all SAEs for the primary endpoint, if the data support such analysis.

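### The only stated objective is that stenting improves outcomes, but the only test with a decision rule is 15-point non-inferiority, so a positive result cannot support the objective

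*SAP*

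**What the plan says.** The Objective(s) row of SAP section 1 has one entry: "To demonstrate that preoperative biliary drainage using self-expanding metal stents (SEMS) improves overall surgical outcomes".

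Section 3.1 names the endpoint: "The rate of serious adverse events is the primary endpoint for the study". Section 3.1.1 then states the test: "Statistical testing will be performed to determine if the rate of complications for the Pre-Operative Biliary Drainage with SEMS group is non-inferior". The null hypothesis is a difference (SEMS minus no drainage) of Δ or more; the alternative is a difference below Δ. The two π in these hypotheses "are the probabilities of having pre-operative, operative and peri-operative complications".

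The decision rule in 3.1.2 begins "If the P value from the exact Farrington-Manning test is <0.05 then the" and ends with SEMS being considered non-inferior. No other conclusion is provided for. On the margin: "The non-inferiority margin (Δ) is 15" percent. On the planning rate, which is the same for both arms: "arm is 37.2%, which was taken from the upper limit of the 95% CI from the meta-analysis described above". Section 1 repeats the hypotheses, rule, margin and planning rate.

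**The concern.** To demonstrate that one strategy improves outcomes, a trial has to reject the hypothesis of no improvement. This plan rejects only the hypothesis that SEMS is worse by 15 points or more. Small harm, no difference and benefit all lie inside its alternative. Followed exactly, the plan ends in non-inferior or not shown, and neither answers the objective.

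A report that sets a successful primary test beside the stated objective would overclaim. A superiority test added after the data are seen would be post hoc. Section 2 foresees use of these analyses in presentations and manuscripts, where that reading would surface.

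The tested quantity also has two names. The endpoint is serious adverse events (sections 1, 3.1 and 3.1.3), but π is defined by complications (sections 1 and 3.1.1). In section 7.3 these are different things. SAEs are defined by seriousness. A separate list gives complication criteria, and it includes grade A pancreaticojejunostomy leakage, which is identified from drain amylase and not from the SAE criteria.

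**Working it through.** **1. Does the plan's own figure reproduce?** Inputs from 3.1.2: 37.2% in both arms, margin 0.15, one-sided alpha 0.05, power 80%.

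- Normal approximation: n = (1.645 + 0.842)² × 2 × 0.372 × 0.628 / 0.15² = 128.4, so 129 per arm.
- Exact Farrington-Manning test, enumerating all binomial outcomes with the maximum size over the null boundary held at 0.05 or less: power is 0.803 at 132 per arm, and 0.797 to 0.799 at 129 to 131.
- Attrition: 132 / 0.90 = 146.7, so 147 per arm.

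The 264 and 294 are sound for non-inferiority.

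**2. Does success under the rule imply improvement?** Take 132 per arm with 49 control events (37.1%, the nearest count to 37.2%). The statistic is z = (p_test − p_control − 0.15) / SE, where SE uses the maximum-likelihood rates constrained to differ by 0.15. The exact p maximises the tail probability over the null boundary.

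| SEMS events | Observed difference | Constrained rates | SE | z | Asymptotic p | Exact p |
|---|---|---|---|---|---|---|
| 55/132 (41.7%) | +4.5 points | 0.472, 0.322 | 0.0595 | −1.756 | 0.040 | 0.042 |
| 56/132 (42.4%) | +5.3 points | 0.476, 0.326 | 0.0596 | −1.627 | 0.052 | 0.055 |

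So the trial can succeed with SEMS observed 4.5 points worse. Under the SAP's own 37.2% in both arms, 27.8% of all trials succeed with more SEMS than control events. That is 0.278 / 0.803 = 0.35, about one success in three.

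**3. Does any other analysis supply a superiority rule?**

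- 5.1 and 5.3: secondary endpoints are listed; post-procedure data are summarised descriptively.
- 5.4 and 5.5: tabulation by gender, and a check of differences between institutions.
- 5.6: the p thresholds (0.20, 0.10) select predictors.
- 5.7: paired t and McNemar tests compare with baseline. A model includes treatment group, and its interaction with time is to be explored. No hypothesis, alpha or success rule is given.
- 5.8: subjects with and without adverse events are compared on time of surgery, hospitalisation and ICU stay, with a treatment interaction. Again there is no hypothesis, alpha or success rule.

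None closes the gap.

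**4. What could a superiority test deliver at this size?** Rates from 3.1.2: 24.2% (SEMS meta-analysis), 37.2% (planning rate), 39% (published no-drainage arm). The 27.2% is an assumption, a 10-point reduction from 37.2%. Normal approximation at n = 132 and one-sided 2.5%: power = Φ[(d − 1.96·√(2p̄(1−p̄)/n)) / √((p₁(1−p₁)+p₂(1−p₂))/n)], where d is the absolute difference and p̄ the mean of the two rates.

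| Rates | Numbers in | Normal approximation | Exact score test |
|---|---|---|---|
| 24.2% vs 37.2% | (0.130 − 0.1113)/0.0562 = 0.33 | 63% | 63% |
| 24.2% vs 39% | (0.148 − 0.1122)/0.0565 = 0.63 | 74% | 73% |
| 27.2% vs 37.2% (assumed) | (0.100 − 0.1127)/0.0572 = −0.22 | 41% | 40% |

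At one-sided 5% the normal approximation gives 74% and 83% for the first two rows, so the choice of alpha matters and must be written down. If the rates are equal, as the sample size assumes, a superiority test rejects only at its type I error rate.

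**The case against.** The objective stands in a summary table that restates a protocol not shown here, and that protocol may word it differently. The operative text is consistently non-inferiority, and 3.1.2 limits a positive result to that conclusion. An overclaim would require a report that ignores the SAP's own rule. No p-value or sample size changes.

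This stands as to weight: it is an inconsistency of wording with consequences for inference, not an error in the analysis. It does not remove the point. The SAP states the objective as its own summary. If the protocol differs, the SAP misstates it; if it agrees, both need the edit.

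A reader might infer from 55 versus 49 events, or from the 27.8%, that the margin or the design is faulty. The figures do not show that. They are ordinary properties of a 15-point margin and would be the same after the objective is reworded. They show only that success does not imply improvement.

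A reader might also infer that the SAP contains no between-group analysis that could bear on benefit. Sections 5.7 and 5.8 do include treatment as a factor, but without a rule that could confirm anything.

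Finally, a reader might draw in the exclusion of subjects with incomplete follow-up in 3.1.3. That is a separate missing-data question and forms no part of this point.

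**Conclusion.** The mismatch is real and rests on the SAP alone: one superiority objective, one non-inferiority test, and nothing that links them. As written, no confirmatory result can support the objective, and the primary test can succeed with SEMS observed up to 4.5 points worse (55 vs 49 of 132, exact p = 0.042). That example assumes 132 evaluable subjects per arm and a control rate close to the planning value.

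Non-inferiority is a legitimate choice here and the sample size is correct for it. What is wrong is what the plan says the trial will demonstrate, together with the two names for the tested parameter. It should be corrected before analysis, and it gives no reason to change the design or the number of subjects.

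**What to change.** **Either, as the minimum:** reword the objective in section 1 as showing that the rate of serious adverse events with SEMS drainage is not worse than with no drainage by 15 percentage points or more. Amend the protocol objective if it reads the same.

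**Or, if a claim of improvement is to stay possible:** prespecify in 3.1.1 one superiority test of the SAE rate (H0: π_test ≥ π_control) in the ITT cohort, done only after non-inferiority is met, with the test and its alpha stated. The fixed order needs no split of alpha. Allow the word improves only for SAEs and only if that test rejects. State that the trial is not sized for it, and give the power as a range (40% to 73% at one-sided 2.5% and 132 per arm, for the three cases above).

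**With either:** use one term for the tested parameter. Define π in sections 1 and 3.1.1 as the probability of at least one SAE. Say in 3.1.2 that the literature complication rates are planning stand-ins for SAE rates. State what role the separate complication criteria in 7.3 play.

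**Cost:** text edits to the SAP and possibly a protocol amendment, with no new data and no change in sample size. The downside is a more modest objective or, under the alternative, one extra prespecified test with limited power.

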2 INTRODUCTION

This statistical plan addresses the planned analyses for the WallFlex Biliary Preoperative Biliary Drainage RCT based on the protocol dated 17 October 2012, Version AC. All of the specified analyses may not be provided in reports to Competent Authorities but may be used for scientific presentations and/or manuscripts. The primary analysis will be based on the data through 120 days post-randomization or 30 days post-surgery whichever comes last.

3 ENDPOINT ANALYSIS

3.1 Primary Endpoint

The rate of serious adverse events is the primary endpoint for the study.

3.1.1 Hypotheses

Statistical testing will be performed to determine if the rate of complications for the Pre-Operative Biliary Drainage with SEMS group is non-inferior to the No Pre-Operative Biliary Drainage group. The null hypothesis is that the complication rate is inferior in the Pre-Operative Biliary Drainage with SEMS versus the No Pre-Operative Biliary Drainage group:

$$H_0: \pi_{\text{test}} - \pi_{\text{control}} \geq \Delta \text{ (Inferior)}$$

$$H_a: \pi_{\text{test}} - \pi_{\text{control}} < \Delta \text{ (Non-inferior)}$$

where π_{test} and π_{control} are the probabilities of having pre-operative, operative and peri-operative complications in the Pre-Operative Biliary Drainage with SEMS arm and No Pre-Operative Biliary Drainage arm respectively, and Δ is defined as the non-inferiority margin.

3.1.2 Sample Size

A literature search of preoperative biliary drainage with self-expanding metal stents in patients with pancreatic or periampullary cancer yielded 8 articles with 305 patients.^{21-24, 27-31}

The following meta-analysis of the probability for pre-operative, operative and post-operative complications was done:

- A rate of 24.2% [95% CI: 13.2%, 37.2%] was calculated using the 8 articles.

The sample size was calculated for a one-sided 0.050 exact Farrington-Manning test using StatXact 9®. If the P value from the exact Farrington-Manning test is <0.05 then the *Pre-Operative Biliary Drainage with SEMS* group will be considered non-inferior to the *No Pre-Operative Biliary Drainage* group. The expected probability of complications in the *Pre-Operative Biliary Drainage with SEMS* arm and *No Pre-Operative Biliary Drainage* arm is 37.2%, which was taken from the upper limit of the 95% CI from the meta-analysis described above and from the only available Level 1 study comparing no drainage to preoperative stenting in which the complication rate was reported to be 39% in the no drainage arm.⁹ The non-inferiority margin (Δ) is 15%. Given these assumptions and a one-sided 5% significance level, $2 \times 132 = 264$ subjects will provide 80% power to reject the null hypothesis, that the *Pre-Operative Biliary Drainage with SEMS* group is inferior to the *No Pre-Operative Biliary Drainage* group.

To compensate for possible loss of subjects after enrollment and complete assessment of inclusion/exclusion criteria, an additional 10% of subjects will be enrolled, for a total of $2 \times 147 = 294$ subjects.

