5.2 Baseline Data

Baseline data will be summarized. Subject demographics, clinical history, risk factors, LFTs, tumor diagnosis, and obstruction symptoms will be summarized using descriptive statistics (e.g., mean, standard deviation, n, minimum, maximum) for continuous variables and frequency statistics for discrete variables.

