5.6 Multivariable Analysis

Univariate and multivariate analyses will be performed to assess possible predictors of the rate of serious adverse events. Possible predictors may include any but not limited to demographic/baseline data and medical history data. Factors from the univariate model with $p \leq 0.20$ will also be modeled multivariately using a stepwise procedure in a generalized linear model or Cox proportional hazards regression model. The significance thresholds for entry and exit into the model will be set to $p < 0.10$.

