5.7 Analysis of LFT's and Obstruction symptoms

For analysis of LFT's and obstruction symptoms, a paired t-test and McNemar's Test will be used to test differences from baseline. The data will also be analyzed using a generalized linear model, including treatment group and baseline covariates as predictors. Interactions between time and treatment group will be explored. Other possible predictors may include any but not limited to demographic/baseline data and medical history data. Different correlation structures will be fit to determine the best model fit.

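### The primary non-inferiority test is valid and adequately powered, but makes no use of baseline values the trial already collects; a short pre-specified adjustment could add modest precision

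*SAP*

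**What the plan says.** SAP 3.1.2 sizes the trial for a "one-sided 0.050 exact Farrington-Manning test" and uses the same test for the decision: "If the P value from the exact Farrington-Manning test is <0.05", the stent arm is declared non-inferior. The assumed rate in each "arm is 37.2%, which was taken from the upper limit of the 95% CI from the meta-analysis". "The non-inferiority margin (Δ) is 15" percentage points, and 264 evaluable "subjects will provide 80% power to reject the null hypothesis". Section 3.1.3 deals with follow-up and missing outcomes; it names no covariate or stratum.

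Baseline and site information appears elsewhere in the SAP:

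- 5.2: demographics, "clinical history, risk factors, LFTs, tumor diagnosis, and obstruction symptoms will be summarized using descriptive statistics" or frequencies.
- 5.5: regression on institution, to justify pooling.
- 5.6: univariate screening and a stepwise model to "assess possible predictors of the rate of serious adverse events". It is not described as the treatment comparison.
- 5.7: a model for LFTs and obstruction symptoms, "including treatment group and baseline covariates as predictors".

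**The concern.** A plan that looks for baseline predictors of serious adverse events in 5.6, and adjusts another treatment comparison for baseline values in 5.7, could use such values in the comparison that decides the trial. Any part of the outcome variation that baseline values explain stays in the standard error of an unadjusted risk difference. Adjustment removes it without changing the hypothesis, the margin, the sample size or the data collected.

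The only multivariable look at the primary outcome is the stepwise search in 5.6. Its covariates are chosen from the data and treatment is not named as a fixed term, so it cannot stand in for a pre-specified adjusted comparison. At stake is a modest amount of precision, not the validity of the conclusion.

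**Working it through.** **Inputs.** From SAP 3.1.2: p = 0.372 in both arms, Δ = 0.15, one-sided α = 0.05, power 80%, 132 per arm, 10% allowance. From the synopsis: 1:1 block randomisation, no stratification factor stated, 7 to 12 sites. Prognostic strength is not given; a covariate with a logit SD of 0.4 to 0.7 (odds ratio about 1.5 to 2.0 per SD) is an assumption.

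**1. The plan's own figure.** Unpooled formula: n = (1.645 + 0.842)² × 2 × 0.372 × 0.628 / 0.15² = 6.183 × 0.4672 / 0.0225 = 128.4, so 129 per arm. The asymptotic Farrington-Manning formula gives 127. The exact unconditional test gives power of 79.7% to 79.9% at 128 to 131 per arm and 80.3% at 132. Then 132 / 0.9 = 146.7, so 147. The stated numbers reproduce.

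**2. Precision without adjustment.** SE = √(2 × 0.372 × 0.628 / 132) = 0.0595, so the 90% interval has a half-width of 1.645 × 0.0595 = 9.8 points.

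**3. What a baseline covariate could remove.** With R² the share of p(1−p) that the covariate explains, the large-sample variance is multiplied by (1 − R²), and power is about Φ(0.15 / [0.0595 √(1 − R²)] − 1.645).

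| Assumed logit SD | R² | SE | Power by formula |
|---|---|---|---|
| 0 | 0 | 0.0595 | 81.0% |
| 0.4 | 0.036 | 0.0584 | 82.2% |
| 0.7 | 0.094 | 0.0566 | 84.2% |

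Like for like, the formula gives about +1 to +3 points. Against the exact test's 80.3% it gives about +2 to +4, because the exact test is slightly conservative.

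**4. Simulation at 132 per arm, one baseline covariate, standardised risk difference.** Variance rises by about 0.4% if the covariate is not prognostic. It falls by about 4% to 9% at logit SD 0.4 to 0.7, with power up by about 2 to 3 points. One-sided size at the margin (52.2% against 37.2%) is 4.8% to 5.0%, subject to simulation error. In subjects, the saving equals 0.04 × 264 ≈ 11 to 0.09 × 264 ≈ 24.

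**5. Adding institution.** Ten site terms cost about 4% in variance when sites do not differ, and size reached 5.35%. A separate simulation used 264 subjects, allocation not stratified by site, and a linear model with site terms and one covariate:

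| Site SD | Covariate odds ratio per SD | Variance change, 7 sites | Variance change, 12 sites |
|---|---|---|---|
| 0 | 1.0 | +2% | +5% |
| 0 | 1.5 | 0% | +2% |
| 0 | 2.0 | −9% | −4% |
| 10 points | 1.0 | 0% | +1% |
| 15 points | 2.0 | −18% | −17% |

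Site terms can cancel the gain from a weak covariate. They pay for themselves only if site rates vary by more than about 10 points.

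**The case against.** **The test is valid and matches its sample size.** This stands in full. Leaving covariates out of a primary test is a legitimate choice, and nothing in the SAP is wrong on this point.

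**The gain is undocumented.** This also stands. A reader might infer that the trial is certain to give up precision, or that adjustment can never cost anything. The SAP gives no prognostic strength to support the first, and the simulated losses contradict the second. Section 5.6 speaks only of possible predictors.

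**The plan does use these data.** A reader might infer that the SAP ignores institution and baseline values, or that the primary comparison alone omits them. Neither is right: 5.5 to 5.7 use them, and the ANOVA in 5.8 also names no baseline covariate.

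**Power is less tight than it looks.** The planning rate is the upper confidence limit of a 24.2% estimate. Exact power at 132 per arm is 88.3% if both arms are at 24.2%, and 87.3% at 37.2% against the cited 39% control rate. The margin over 80% is thin only under the planning assumption, so the trial should not be read as underpowered.

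**An asymptotic test may exceed 5%.** This matters for large models. In a simulation with site terms, size ran as high as 5.9%. Moving one-sided α from 5% to 5.9% alone would lift power from 80.0% to 82.2%, as much as a weak covariate gains. It does not hold for a short baseline-only model, where size stayed at 4.8% to 5.0%. The adjusted test is still not exact, which is a fair reason to keep the exact test as the decision rule.

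**Conclusion.** The point holds as an optional improvement of low severity. The primary comparison uses no baseline covariate, although bilirubin and tumour diagnosis are already collected, and a short pre-specified adjustment keeps the same hypothesis on the same scale. The size is roughly zero if the covariates are not prognostic, and about 4% to 9% lower variance (about 2 to 3 power points) under the assumed logit SD of 0.4 to 0.7. At those values the 90% half-width of 9.8 points would shrink to about 9.8 × √0.96 = 9.6 or 9.8 × √0.91 = 9.3.

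Two limits apply. The simulation used one continuous covariate, not the exact pair proposed below. Eligibility requires bilirubin of at least 100 µmol/L, which narrows its range and may weaken it as a predictor. Adding institution by default is not supported.

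**What to change.** In 3.1.3, before outcomes are seen by arm:

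1. Pre-specify a standardised (marginal) risk difference from a logistic model with treatment, baseline bilirubin (scale stated) and tumour diagnosis as recorded at baseline, not from surgical pathology. Compare its one-sided 95% upper bound with 15%.
2. Name one decision rule. Either the adjusted bound decides and the exact Farrington-Manning test is reported alongside, or, if exact size control is wanted, the exact test decides and the adjusted estimate is the named key supportive result.
3. Include institution only if randomisation was stratified by it, or with small sites combined by a stated rule.
4. Do not take covariates from the stepwise search in 5.6.

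With three tumour groups the model has four terms besides the intercept (treatment, bilirubin, two indicators), against about 264 × 0.372 ≈ 98 expected events. The cost is a paragraph and one model, with no new data and no change to margin or sample size. The downside is that the adjusted test is asymptotic rather than exact, and about ten site terms, if added, cost about 4% in variance when sites do not differ.
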